**RESTRICTED**

	SPONSOR: Scandinavian Biopharma Holding AM (SBH)	PROTOCOL NUMBER: OEV-131	PROTOCOL TITLE: Pre-Study of wild type Enterotoxigenic E.coli (ETEC) Strain for Verification of a planned Challenge Dose	VERSION NO: 1.0
				VERSION DATE: 14JUN2024

#### 14.3.1.1 Solicited Adverse Events

**Table 22: Number and Percentage of Subjects Experiencing ETEC Disease-Specific Solicited Events with 95% Confidence Intervals by Symptom - Full Analysis Set**

Sign or Symptom	All Subjects (N=X)		
	n	%	95% CI a
Any Sign or Symptom	x	xx	x.X, x.X
Malaise			
Loss of Appetite			
Headache			
Chills			
Nausea			
Abdominal Pain			
Abdominal Cramps			
Myalgia			
Arthralgia			
Urgency of Defecation			
Lightheadedness			
Diarrhea			
Hypovolemia			
Fever			
Vomiting			

Notes: N = Number of subjects in the Full Analysis Set; n = Number of subjects reporting the corresponding sign or symptom.

a Exact binomial confidence interval calculated using Clopper-Pearson methodology.

**RESTRICTED**

SPONSOR: Scandinavian Biopharma Holding AM (SBH)	PROTOCOL NUMBER: OEV-131	PROTOCOL TITLE: Pre-Study of wild type Enterotoxigenic E.coli (ETEC) Strain for Verification of a planned Challenge Dose	VERSION NO: 1.0
			VERSION DATE: 14JUN2024

**Table 23: Number and Percentage of Subjects Experiencing ETEC Disease Specific Solicited Events by Symptom and Maximum Severity - Full Analysis Set**

Sign or Symptom	Severity	All Subjects (N=X)	
		n	%
Any Sign or Symptom	None	x	xx
	Mild	x	xx
	Moderate	x	xx
	Severe	x	xx
	Potentially Life-Threatening	x	xx
Malaise	None		
	Mild		
	Moderate		
	Severe		
	Potentially Life-Threatening		
Loss of Appetite	None		
	Mild		
	Moderate		
	Severe		
	Potentially Life-Threatening		
[Continue with remaining solicited symptoms...]	None		
	Mild		
	Moderate		
	Severe		
	Potentially Life-Threatening		

Notes: N = Number of subjects in the Full Analysis Set. n = Number of subjects with reported event. Severity is the maximum severity reported over all solicited symptoms post challenge for each subject.

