³ Moderate to severe ETEC illness includes mild diarrhea with moderate to severe GI symptoms

⁴ During 0-48h after challenge

⁵ Moderate or severe nausea, vomiting, anorexia, or abdominal pain/cramps

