## 7.3. ETEC Disease-Specific Solicited Events

Number and percentage of subjects experiencing ETEC disease-specific solicited events are presented by symptom with 95% confidence intervals in [Table 22](#), and by symptom and maximum severity in [Table 23 and Figure 5](#). Number and percentage of subjects experiencing ETEC disease specific solicited events by Study Day are presented in [Table 24](#).

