**RESTRICTED**

	SPONSOR: Scandinavian Biopharma Holding AM (SBH)	PROTOCOL NUMBER: OEV-131	PROTOCOL TITLE: Pre-Study of wild type Enterotoxigenic E.coli (ETEC) Strain for Verification of a planned Challenge Dose	VERSION NO: 1.0
				VERSION DATE: 14JUN2024

**Table 24: Number and Percentage of Subjects Experiencing Solicited Events by Symptom, Severity and Days - Full Analysis Set**

Sign or Symptom	Severity	Day 1 (N=X)		Day 2 (N=X)		Day 3 (N=X)		Day 4 (N=X)		Day 5 (N=X)		Day 6 (N=X)		Day 7 (N=X)		Day 8 (N=X)		Day 9 (N=X)	
		n	%	n	%	n	%	n	%	n	%	n	%	n	%	n	%	n	%
Any Sign or Symptom	None																		
	Mild																		
	Moderate																		
	Severe																		
	Potentially Life-Threatening																		
	Not Reported																		
Malaise	None																		
	Mild																		
	Moderate																		
	Severe																		
	Potentially Life-Threatening																		
	Not Reported																		
Loss of Appetite	None																		
	Mild																		
	Moderate																		
	Severe																		
	Potentially Life-Threatening																		
	Not Reported																		
[Continue with remaining solicited symptoms...]	None																		
	Mild																		
	Moderate																		
	Severe																		
	Potentially Life-Threatening																		
	Not Reported																		

Notes: N = Number of subjects in the Full Analysis Set; n = Number of subjects with reported event.

Severity is the maximum severity reported post challenge for each subject on each day.

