#### 14.3 Safety Data

**Figure 5: Maximum Severity of ETEC Diseases-Specific Solicited Events by Sign or Symptom - Full Analysis Set**

[figure not shown]
[Implementation Note: A generic sample figure is shown below. The bar chart should be presented in a single-paneled figure labeled as “All Subjects (N=X)”, where N = the number of subjects in the Full Analysis Set. Axes should be labeled as follows: y-axis label: Sign or Symptom, x-axis label: Percentage of Subjects (%). Subjects are counted at most once per sign or symptom at the maximum severity reported.]

SPONSOR: Scandinavian Biopharma Holding AM (SBH)	PROTOCOL NUMBER: OEV-131	PROTOCOL TITLE: Pre-Study of wild type Enterotoxigenic E.coli (ETEC) Strain for Verification of a planned Challenge Dose	VERSION NO: 1.0
			VERSION DATE: 14JUN2024

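### The note under SAP Table 23 takes each subject's maximum severity over all solicited symptoms, which is right only for the Any Sign or Symptom rows and would inflate the individual symptom rows if followed

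*SAP*

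**What the plan says.** Table numbers here are those printed on the shells and used in the SAP text; the list of tables in Appendix A runs one higher.

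- **Table 23, title:** "Number and Percentage of Subjects Experiencing ETEC Disease Specific Solicited Events by Symptom and Maximum Severity - Full Analysis Set". The shell opens with an Any Sign or Symptom block, followed by a block for each symptom running from none to potentially life-threatening.
- **Table 23, note:** "n = Number of subjects with reported event", and then "Severity is the maximum severity reported over all solicited symptoms post challenge for each subject". Nothing limits the second statement to the first block.
- **SAP 7.3:** solicited events are presented "and by symptom and maximum severity in" Table 23 and Figure 5, named together.
- **Figure 5, implementation note:** "Subjects are counted at most once per sign or symptom at the maximum severity reported".
- **Table 24, note (same events by day):** "Severity is the maximum severity reported post challenge for each subject on each day". It does not pool over symptoms, but it does not say the maximum is taken within a symptom either.
- **SAP 2.8.3.2:** diarrhea, fever and vomiting are graded; hypovolemia is recorded as present or not, without a severity grade.

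**The concern.** The note is the written derivation rule for the table and would be printed beneath it. It defines one number per subject, whereas the table needs one number per subject and symptom. A programmer who follows the note would fill the malaise, headache or nausea rows with grades that belong to a different symptom. One who follows the title would produce correct counts under a footnote that misdescribes them. Table 23 is the SAP's tabular summary, over the whole post-challenge period, of how severe each solicited symptom was at this dose, so its symptom-level grades should mean what they appear to mean.

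**Working it through.** The plan states no figure to reproduce. The check compares the two counting rules.

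**Step 1: direction.** Let g(i,s) be subject i's highest grade for symptom s. Figure 5 and SAP 7.3 call for g(i,s). The Table 23 note gives max over s of g(i,s). The second is never below the first, so the note can only raise a grade or leave it unchanged.

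**Step 2: four invented subjects** (0 none, 1 mild, 2 moderate, 3 severe). The last three columns apply the note to symptoms the subject reported.

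| Subject | Diarrhea, own | Malaise, own | Headache, own | Diarrhea, note | Malaise, note | Headache, note |
|---|---|---|---|---|---|---|
| A | 3 | 1 | 0 | 3 | 3 | 0 |
| B | 2 | 0 | 1 | 2 | 0 | 2 |
| C | 1 | 2 | 0 | 2 | 2 | 0 |
| D | 0 | 0 | 0 | 0 | 0 | 0 |

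Subject A's mild malaise becomes severe and subject B's mild headache becomes moderate. Subject C shows that diarrhea can be the symptom that is upgraded: mild diarrhea becomes moderate because of the malaise. Table 13, which reports maximum diarrhea severity on its own, would still show mild for C, so the two tables would disagree.

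**Step 3: hypovolemia.** It is among the 15 signs and symptoms listed in Table 22, and so among the remaining symptoms Table 23 is to continue with. It has no grade of its own. The note would give it the grade of the subject's worst graded symptom, contrary to SAP 2.8.3.2.

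**Step 4: an illustration of size.** N = 25 to 30 comes from Protocol section 9. Everything else is assumed: a symptom reported by r = 50% of subjects; a share q = 20% to 50% of those reports moderate or worse; moderate-or-worse diarrhea in d = 60% to 81%; independence; and diarrhea the only other symptom that can raise the grade. The range for d borrows the protocol's rate for moderate-to-severe ETEC illness as a stand-in; it is not a documented diarrhea rate.

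- Per-symptom rule: expected number moderate or worse = N × r × q.
- Note, reported symptoms only: N × r × [1 − (1 − d)(1 − q)].

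At N = 30:
- q = 20%: 30 × 0.5 × 0.2 = 3.0 by symptom. Under the note, 15 × [1 − 0.40 × 0.80] = 10.2 at d = 60%, and 15 × [1 − 0.19 × 0.80] = 12.7 at d = 81%.
- q = 50%: 30 × 0.5 × 0.5 = 7.5 by symptom. Under the note, 15 × [1 − 0.40 × 0.50] = 12.0 at d = 60%, and 15 × [1 − 0.19 × 0.50] = 13.6 at d = 81%.

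At N = 25 the same formulas give 2.5 against 8.5 to 10.6, and 6.2 against 10.0 to 11.3.

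**The case against.** The best defence is that the intended rule is plain from the surroundings. The title, the block for each symptom, SAP 7.3 and Figure 5 all say per symptom, and the note makes sense for the first block. A careful programmer would probably do the right thing, and a mismatch with Figure 5 would be easy to see. This lowers the chance of wrong counts. It does not correct the note, and no other part of the SAP does.

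Three stronger readings are tempting, and the documents do not support them.

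- *A reader might infer that every symptom inherits the worst grade, reported or not.* The same note defines n as subjects with the reported event, so the natural literal reading regrades only what was reported. If all subjects inherited, the Step 4 assumptions would give N × [1 − (1 − d)(1 − rq)] = 19.2 to 25.7 of 30, but that is not the reading to argue from.
- *A reader might infer that diarrhea usually sets the grade.* Neither document says which symptom is worst. The 60% to 81% in Protocol 9.2 is a rate of illness, not of diarrhea grade: "Moderate to severe ETEC illness includes mild diarrhea with moderate to severe GI symptoms". Protocol Table 3 also reports a moderate or severe key symptom (nausea, vomiting, anorexia, or abdominal pain or cramps) in 8 of 16 subjects in one trial.
- *A reader might infer that symptom severity would be hidden, or a secondary endpoint spoiled.* The secondary endpoint is occurrence, which Table 22 reports with confidence intervals and the note does not touch. Figure 5, Table 24, Listing 11 and, for five symptoms, Listing 7 would still show severity by symptom.

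**Conclusion.** The note is wrong as written for the individual symptom blocks and right for the Any Sign or Symptom block. Followed literally, it would raise the grade of any reported symptom milder than the subject's worst one, and it would grade hypovolemia. Table 23 would then conflict with Figure 5 and SAP 7.3, and with Table 13 wherever another symptom outranks diarrhea.

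The direction is certain; the size depends on the data. The Step 4 figures rest on assumed reporting rates, assumed severity and independence, and correlation between symptoms could move them either way. The consequence is limited to one descriptive table. The primary endpoint and its interval, the disease severity score and Table 22 do not use this rule, and no formal testing is planned. The correction is worth making because the rule is explicit, the error is one-sided and the remedy is trivial.

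**What to change.** Replace the severity sentence under Table 23 with wording such as: *In the rows for a given sign or symptom, severity is the highest grade recorded for that sign or symptom after challenge in each subject. In the Any Sign or Symptom rows, it is the highest grade across all graded solicited signs and symptoms.*

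Show hypovolemia as present or absent only, in keeping with SAP 2.8.3.2. Reword the Table 24 note in the same way, adding that the maximum is taken within each day.

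The cost is one sentence in each of two table shells and one simplified block. No data collection or other analysis changes. Table 23 carries no topline asterisk, so the topline report is not affected.

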**RESTRICTED**

	SPONSOR: Scandinavian Biopharma Holding AM (SBH)	PROTOCOL NUMBER: OEV-131	PROTOCOL TITLE: Pre-Study of wild type Enterotoxigenic E.coli (ETEC) Strain for Verification of a planned Challenge Dose	VERSION NO: 1.0
				VERSION DATE: 14JUN2024

**Table 24: Number and Percentage of Subjects Experiencing Solicited Events by Symptom, Severity and Days - Full Analysis Set**

Sign or Symptom	Severity	Day 1 (N=X)		Day 2 (N=X)		Day 3 (N=X)		Day 4 (N=X)		Day 5 (N=X)		Day 6 (N=X)		Day 7 (N=X)		Day 8 (N=X)		Day 9 (N=X)	
		n	%	n	%	n	%	n	%	n	%	n	%	n	%	n	%	n	%
Any Sign or Symptom	None																		
	Mild																		
	Moderate																		
	Severe																		
	Potentially Life-Threatening																		
	Not Reported																		
Malaise	None																		
	Mild																		
	Moderate																		
	Severe																		
	Potentially Life-Threatening																		
	Not Reported																		
Loss of Appetite	None																		
	Mild																		
	Moderate																		
	Severe																		
	Potentially Life-Threatening																		
	Not Reported																		
[Continue with remaining solicited symptoms...]	None																		
	Mild																		
	Moderate																		
	Severe																		
	Potentially Life-Threatening																		
	Not Reported																		

Notes: N = Number of subjects in the Full Analysis Set; n = Number of subjects with reported event.

Severity is the maximum severity reported post challenge for each subject on each day.

**RESTRICTED**

DOCUMENT REF.: SOP-ST-01 LAST REVISION DATE: N/A VERSION NO.: 1.0	DOCUMENT NAME: Statistical Analysis Plan			
	SPONSOR: Scandinavian Biopharma Holding AM (SBH)	PROTOCOL NUMBER: OEV-131	PROTOCOL TITLE: Pre-Study of wild type Enterotoxigenic E.coli (ETEC) Strain for Verification of a planned Challenge Dose	VERSION NO: 1.0 VERSION DATE: 14JUN2024

#### 14.3.1.2 Unsolicited Adverse Events

**Table 25: Summary of Unsolicited Adverse Events by MedDRA System Organ Class and Preferred Term - Full Analysis Set**

MedDRA System Organ Class	MedDRA Preferred Term	All Subjects (N=X)		
		n	%	Events
Any SOC	Any PT	x	xx	x
[SOC 1]	Any PT			
	[PT 1]			
	[PT 2]			
[SOC 2]	Any PT			
	[PT 1]			
	[PT 2]			
...	...			

Note: N = Number of subjects in the Full Analysis Set; n = Number of subjects with reported event; Events = Total frequency of events reported.

**RESTRICTED**

	SPONSOR: Scandinavian Biopharma Holding AM (SBH)	PROTOCOL NUMBER: OEV-131	PROTOCOL TITLE: Pre-Study of wild type Enterotoxigenic E.coli (ETEC) Strain for Verification of a planned Challenge Dose	VERSION NO: 1.0
				VERSION DATE: 14JUN2024

**Table 26: Unsolicited Adverse Events by MedDRA System Organ Class and Preferred Term, Maximum Severity, and Relationship to Challenge - Full Analysis Set**

MedDRA System Organ Class	MedDRA Preferred Term	Severity	All Subjects (N = X)								
			Related to Challenge			Not Related to Challenge			All Events		
			n	%	Events	n	%	Events	n	%	Events
Any SOC	Any PT	Any Severity	x	xx	x	x	xx	x	x	xx	x
		Mild	x	xx	x	x	xx	x	x	xx	x
		Moderate	x	xx	x	x	xx	x	x	xx	x
		Severe	x	xx	x	x	xx	x	x	xx	x
		Potentially Life-Threatening	x	xx	x	x	xx	x	x	xx	x
[SOC 1]	[PT 1]	Any Severity	x	xx	x	x	xx	x	x	xx	x
		Mild	x	xx	x	x	xx	x	x	xx	x
		Moderate	x	xx	x	x	xx	x	x	xx	x
		Severe	x	xx	x	x	xx	x	x	xx	x
		Potentially Life-Threatening	x	xx	x	x	xx	x	x	xx	x
	[PT 2]	Any Severity	x	xx	x	x	xx	x	x	xx	x
		Mild	x	xx	x	x	xx	x	x	xx	x
		Moderate	x	xx	x	x	xx	x	x	xx	x
		Severe	x	xx	x	x	xx	x	x	xx	x
		Potentially Life-Threatening	x	xx	x	x	xx	x	x	xx	x
...	...										
Note: N = Number of subjects in the Full Analysis Set; n = Number of subjects reporting adverse events of the corresponding SOC, PT, maximum severity, and relationship to challenge.											

**RESTRICTED**

DOCUMENT REF.: SOP-ST-01 LAST REVISION DATE: N/A VERSION NO.: 1.0	DOCUMENT NAME: Statistical Analysis Plan			
	SPONSOR: Scandinavian Biopharma Holding AM (SBH)	PROTOCOL NUMBER: OEV-131	PROTOCOL TITLE: Pre-Study of wild type Enterotoxigenic E.coli (ETEC) Strain for Verification of a planned Challenge Dose	VERSION NO: 1.0 VERSION DATE: 14JUN2024

**Table 27: Summary of Adverse Events Leading to Study Withdrawal by MedDRA System Organ Class and Preferred Term - Full Analysis Set**

MedDRA System Organ Class	MedDRA Preferred Term	All Subjects (N=X)	
		n	%
Any SOC	Any PT	x	xx
[SOC 1]	Any PT		
	[PT 1]		
	[PT 2]		
[SOC 2]	Any PT		
	[PT 1]		
	[PT 2]		
...	...		

Note: N = Number of subjects in the Full Analysis Set; n = Number of subjects with reported event.

**RESTRICTED**

	SPONSOR: Scandinavian Biopharma Holding AM (SBH)	PROTOCOL NUMBER: OEV-131	PROTOCOL TITLE: Pre-Study of wild type Enterotoxigenic E.coli (ETEC) Strain for Verification of a planned Challenge Dose	VERSION NO: 1.0
				VERSION DATE: 14JUN2024

#### 14.3.2 Displays of Vital Signs

**Table 28: Oral Temperature by Maximum Severity and Study Day - Full Analysis Set**

Study Day	N	Normal		Mild		Moderate		Severe		Potentially Life-Threatening	
		n	%	n	%	n	%	n	%	n	%
Baseline (Day -1)	x	x	xx	x	xx	x	xx	x	xx	x	xx
Day 1 (30 minutes after challenge)											
Day 2											
Day 3											
Day 4											
Day 5											
Day 6											
Day 7											
Day 8											
Day 9											
Day 29											
Max Severity Post Baseline											

Notes: N = Number of subjects in the Full Analysis Set with available data at the corresponding time point; N is the denominator for percentages; n = Number of subjects with maximum oral temperature of the corresponding severity on the given study day.

The “Max Severity Post Baseline” rows indicate the maximum severity experienced by each subject at any time point post baseline, including unscheduled assessments. If a subject has only ungraded results post baseline, their maximum severity is considered “None”.

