9.5.2.4 Vital signs

Vitals signs, including systolic and diastolic blood pressure (mmHg), pulse (beats/minute) and temperature (°C), will be measured at least 3 times daily during in-patient period. In addition, postural (supine to standing) blood pressure and pulse will be measured if indicated by clinical signs and symptoms. If tolerated, postural vital signs will be measured after the subject has been supine for 2 minutes, then again after 2 minutes of standing. Vital signs may be measured more frequently if the subject is ill or per the orders of the PI or designee.

Only key vital signs (measured on Day -1 and on Day 1 after challenge) will be collected in the eCRF. Additional vital signs may be collected in the eCRF per the investigator's clinical decision; clinical findings may be reportable as AEs per provider discretion.

The following vital sign measurements are concerning for hypovolemia and will be closely monitored:

- Supine systolic blood pressure <90 mmHg.
- Postural decrease in systolic BP of >20 mmHg.
- Postural decrease in diastolic BP of >20 mmHg.
- Postural increase in pulse >30 beats/min.

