9.7.3.2 Vital signs and Physical examination findings

Key vital signs (those measured on Day -1 and 30 minutes after challenge) will be summarized.

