#### **2.8.5. Vital Signs**

Systolic and diastolic blood pressure (mmHg), pulse (beats/minute) and temperature (°C), will be measured at least 3 times daily during in-patient period. In addition, postural (supine to standing) blood pressure and pulse will be measured if indicated by clinical signs and symptoms. If tolerated, postural vital signs will be measured after the subject has been supine for 2 minutes, then again after 2 minutes of standing. Vital signs may be measured more frequently if the subject is ill or per the orders of the PI or designee.

Vital signs will be graded according to [Table 5](#).

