### 3.5. Handling of Missing Data

All attempts will be made to collect all data per protocol. As missing data are expected to be minimal, no imputation will be performed for missing values. Any data point that appears to be erroneous or inexplicable based on clinical judgment will be investigated.

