## 7.6. Vital Signs

Oral temperature is presented by assessment, severity and study day ([Table 28](#)). Individual subject listings of vital signs are presented in [Listing 15](#).

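### SAP Table 28 gives daily temperature severity as a percentage of subjects with data, but after Day 1 the eCRF holds temperatures only where an investigator chose to enter them

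*SAP*

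**What the plan says.** Table numbers here are those on the SAP mock-ups; the list of tables in Appendix A numbers the same displays one higher.

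**Measurement.** Protocol 9.5.2.4 and SAP 2.8.5 agree that vital signs, including temperature, "will be measured at least 3 times daily during in-patient period".

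**Data entry.** Protocol 9.5.2.4 then limits what reaches the database: "Only key vital signs (measured on Day -1 and on Day 1 after challenge) will be collected in the eCRF". For everything else, "Additional vital signs may be collected in the eCRF per the investigator's clinical decision". SAP 2.8.5 repeats the measurement rule but not this limit.

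**Planned summary.** Protocol 9.7.3.2 matches the entry rule: "Key vital signs (those measured on Day -1 and 30 minutes after challenge) will be summarized". SAP 7.6 goes further: "Oral temperature is presented by assessment, severity and study day". The Table 28 shell has rows for Day -1, Day 1 at 30 minutes, each of Days 2 to 9, Day 29, and the maximum severity after baseline. Its footnote reads "N = Number of subjects in the Full Analysis Set with available data at the corresponding time point; N is the denominator for percentages".

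**Missing data.** SAP 3.5 states: "As missing data are expected to be minimal, no imputation will be performed for missing values".

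**Other fever displays.** Fever is a solicited event in Tables 22-24. Table 22 defines its denominator as the whole analysis set: "N = Number of subjects in the Full Analysis Set; n = Number of subjects reporting the corresponding sign or symptom".

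**The concern.** An available-data denominator is reasonable when absence of a value has nothing to do with the value. Here absence is the protocol's default for every day after Day 1, and presence depends on a clinical decision. A subject who feels ill or has a raised temperature is more likely to prompt an entry than a well subject. The Day 2-9 rows would then describe mainly the subjects who caused concern, while the percentages read as if they described the cohort.

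At stake is a misleading safety percentage in a study meant to characterise this challenge dose before phase 3. Table 28 is the SAP's only summary table of vital signs. It could also show, for the same subjects and the same day, a fever percentage that conflicts with Table 24.

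**Working it through.** Table 28 is an empty shell, so the plan has no figure to reproduce. The check has two parts.

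**1. Rows against the entry rule**

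| Table 28 row | Required in the eCRF (protocol 9.5.2.4)? | In the protocol's summary (9.7.3.2)? |
|---|---|---|
| Day -1 | Yes | Yes |
| Day 1, 30 minutes after challenge | Yes | Yes |
| Days 2 to 9 | No, by clinical decision | No |
| Day 29 | No, by clinical decision | No |
| Maximum after baseline | Day 1 reading required, later readings not | No |

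Nothing in SAP 2.8.5, 3.5 or 7.6 says that all daily temperatures will be entered, or that Table 28 draws on another source.

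**2. Size of the effect on a daily row**

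Inputs:
- N = subjects under observation that day. I use 25, the protocol's minimum enrolment (9.3.4).
- f = febrile subjects that day. Assumed to be 3.
- p = chance that a febrile subject's temperature is entered. Assumed to be 1.
- q = chance that an afebrile subject's temperature is entered. Unknown, so varied.

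At the expected denominator, the printed percentage is

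pf / [pf + q(N − f)].

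This equals the true f/N only when p = q, that is, when entry does not depend on fever. It is too high when p > q.

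With p = 1, f = 3 and N = 25 the true value is 3/25 = 12.0%. The table would print:

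| q | Expected denominator, 3 + 22q | Printed |
|---|---|---|
| 1 | 25.0 | 12.0% |
| 0.5 | 14.0 | 21.4% |
| 0.25 | 8.5 | 35.3% |
| 0.1 | 5.2 | 57.7% |
| 0 | 3.0 | 100% |

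With N = 30, the protocol's maximum, and f = 3 (true value 10.0%), the corresponding figures are 10.0%, 18.2%, 30.8%, 52.6% and 100%. On a day with no febrile subject, f = 0 and nothing is overstated at any q above 0.

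**The case against.** Most of the case on the other side concerns scope, and much of it stands.

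- **The direction is inferred.** No passage says which temperatures will be entered, and the data management plan is a separate document. If the eCRF in practice holds every daily reading, the selection disappears. This stands, which is why the overstatement is called probable and its size is given only as a range.
- **The table discloses its own N.** Each row prints its denominator, and Listing 15 lists individual vital signs. A careful reader would notice a row with N = 4. That softens the problem but does not make the percentage meaningful.
- **The protocol does not forbid extra rows.** Section 9.7.3.2 says what will be summarised, and 9.7 leaves detail to the SAP. This stands: the added rows are not a breach in themselves. The fault is that the required data do not support them.
- **The maximum row.** A reader might infer that it fails too, because subjects with no later entry are classified on the 30-minute reading. If febrile readings are the ones entered, however, the row comes out close to febrile over all challenged, 3/25 = 12% in the example, which is the right figure.
- **A full-analysis-set denominator for every day.** A reader might infer that this is the cure. The documents do not support it for late inpatient days. Protocol 9 and 9.5.6.7 allow early discharge, and solicited events are collected only until discharge (9.5.3.1.4). Early antibiotics, which can lead to early discharge, were given to 12/15 (80%) and 8 of 16 (50%) in the two earlier groups with data (protocol Table 3). Dividing by everyone challenged would count discharged subjects as afebrile.

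**Conclusion.** The point holds for the Day 2-9 and Day 29 rows. Followed as written, the two documents give those rows a denominator selected by clinical decision, and the SAP's expectation of minimal missing data does not fit a field that is optional by design. The likely direction is upward. For a true 12% the printed value could be about 21% to 58% over q = 0.5 to 0.1, assuming that all febrile readings are entered.

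The reach is limited to one descriptive table. A reader might infer that the fever endpoint, the disease severity score or the topline results are affected. The documents do not support that: fever occurrence is reported in Tables 22-24, the score's individual data are in Listing 7 with nothing linking them to Table 28, Table 28 is not marked for the topline report, and the primary endpoint rests on stool output and adjudication. The change is still worth making before the tables are produced, because it costs little and removes a percentage that could mislead.

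**What to change.** **Preferred, a change to SAP table shells and footnotes only:**

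1. Limit the percentage rows of Table 28 to Day -1 and 30 minutes after challenge, in line with protocol 9.7.3.2. Leave any other entered temperatures to Listing 15.
2. Take fever by day from the solicited-event records in Table 24. Define each day's N as subjects still under inpatient observation that day, and show discharged subjects in the table's existing Not Reported row, outside the denominator. Table 24's footnote now defines N as the full analysis set and would need amending.
3. Keep the full analysis set as denominator for ever having fever and for maximum severity (Tables 22 and 23).

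**Alternative:** keep the daily rows, but only if the daily maximum temperature, already measured, is entered for every inpatient. That is 8 extra entries per subject for Days 2 to 9, or 9 with the Day 29 reading: between 25 × 8 = 200 and 30 × 9 = 270 values in all. It also changes the entry rule in protocol 9.5.2.4, so it costs more than the shell change.
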